Analysis Plan: We will measure coronary plaque volume using CCTA images at both baseline and 12-months post-treatment initiation. The primary endpoint will be (1) total coronary plaque volume (continuous). Secondary endpoint will be non-calcified coronary plaque volume (continuous). Other outcome measures include (1) calcified plaque volume (continuous), (2) low-attenuation plaque volume (continuous), (3) coronary artery calcification score (continuous), and (4) coronary vessel stenosis (ordinal). The change in endpoint metrics between baseline and 12-month will be estimated for leuprolide versus relugolix versus no ADT. Data transformation to fit statistical assumptions will be done as needed. In addition, we will implement multivariable models that control for potential confounders (e.g. age, statin medication use) using general linear regression and/or logistic regression.

Power: We hypothesized that there will be significantly greater total plaque burden (i.e. summation of total plaque volume of all major coronary territories) increase from baseline to month 12 following GNRHa versus no ADT or relugolix. Using a standard deviation of 30 mm³ for the change in total plaque volume from scans obtained at two time points approximately 12 months apart in the study, 60 participants (30 in each comparative treatment arm) with both baseline and month 12 CCTA would provide 80% power to detect a difference of ≥ 20 mm³ in the change in total plaque volume [$P(X>Y) 0.72$] from baseline to 12 months.

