Analysis Plan: The correlation among baseline genomic biomarkers, inflammatory biomarkers, and proteomic biomarkers will be described using Spearman Correlation Coefficient for all patients and by treatment group separately. The association of genomic alterations with CV injury metrics (as defined in Aim 1) will be handled by similar statistical strategy as in Subaim 1.2. Additionally, the association of genetic aberrations with peripheral immune responses (as in Aim 2) will be carried out by similar statistical strategy as in Aim 2.

Other statistical considerations:

Safety Population: All patients receiving at least one dose of GNRHa or Relugolix (for parallel randomized arms) or radiation alone (for parallel single cohort arm) will be considered evaluable for safety analyses.

Intent-to-Treat Population: Patients who are evaluable for safety and who are furthermore evaluable at 12-month CCTA assessment will be considered evaluable for correlative biomarker analyses.

Safety Analysis: All AEs experienced data will be described by summary statistics. Adverse events will be assessed according to CTCAE version 5.0 and will be evaluated by grade, attribution, and organ class. Adverse event listings and tabulated summaries of categorized AEs will be generated for all patients collectively and will be summarized by arms. Vital signs and laboratory data will be summarized for changes over time on study.

Stopping Rule: The two ADT test agents are FDA-approved drugs that are used in clinical practice, and hence no stopping rule for safety is in place officially.

7. Data Specimen Banking

To achieve Aims 2 and 3 discussed above, peripheral blood specimens will be collected longitudinally four times for each enrolled patient (i.e. pre-treatment, 3 months, 6 months, 12 months).

Draw 1 (pre)	Draw 2 (3mo)	Draw 3 (6mo)	Draw 4 (12mo)
Pre-ADT	2-4 months post-ADT initiation	6-8 months post-ADT initiation	12-15 months post-ADT initiation

The blood is collected and processed according to the standard operating practices and regulatory parameters of the Winship biorepository and under the guidance of a board-certified pathologist.

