- Emory Research Management System (ERMS; <https://erms.emory.edu>) Enrollment Fax Cover

The WCSR will enter the subject into the OnCore Research Management System, which is the system of record for Winship Cancer Institute Clinical Trials.

Eligible patients will be enrolled on study centrally at Winship Cancer Institute by the Study Coordinator. When all required test results are available, complete the eligibility checklist and provide the checklist and the supporting documentation to the IRB approved investigator for review and sign-off. Once the

Protocol Title: Mechanism and Predictors of Cardiotoxicity after Prostate Cancer Treatment: A Parallel Cohort and Randomized Trial Comparing Radiation Alone, Radiation plus Leuprolide, and Radiation plus Relugolix

investigator (sub-investigator, Co-Investigator) has signed the eligibility checklist, enrollment may proceed. Oncore and ERMS must be updated to reflect eligibility and on treatment status.

14. Withdrawal of Participants

Participation in the study should continue until one of the following criteria applies:

- Intercurrent illness that prevents delivery of planned radiation therapy or ADT
- Unacceptable treatment-related adverse event(s), including patient death
- Withdrawal of informed consent (subject's decision to withdraw for any reason)
- Noncompliance with treatment plan, including delays to treatment or acquisition of additional diagnostic imaging that significantly exceeds the proposed timeline of study events
- General or specific changes in the patient's condition that render the patient unacceptable to receive further treatment in the judgment of the investigator
- Lost to follow up. In the event of a patient's withdrawal, the Investigator will make every effort to complete the End of Treatment/follow-up procedures specified in the Schedule of Events.

15. Risk to Participants

Radiation therapy +/- hormone therapy (either GNRHa or relugolix) are FDA-approved, guideline-supported standard treatments for prostate cancer. There is no additional risk associated with treatment on study, including the randomized portion of treatment (i.e. GNRHa with Lupron/Trelstar and Relugolix are acceptable ADT options for men with prostate cancer undergoing radiation therapy). There is no additional risk associated with blood draws (which will correspond to blood draws taken at standard clinical intervals to minimize additional appointment or peripheral venous sticks).

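### Section 14 ends study participation, not just treatment, for treatment-related reasons, so the 12-month CCTA that forms the primary endpoint is not assured for these men

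*Combined protocol and SAP*

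**What the plan says.** Section 14 (Withdrawal of Participants) opens with "Participation in the study should continue until one of the following criteria applies" and lists six criteria. Two are ordinary study-exit reasons: withdrawal of consent and loss to follow-up. The other four concern treatment:

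- an intercurrent illness that prevents the planned radiation or ADT;
- "Unacceptable treatment-related adverse event(s), including patient death";
- "Noncompliance with treatment plan, including delays to treatment or acquisition of additional diagnostic imaging that significantly exceeds the proposed timeline of study events";
- a change in the man's health that, as the investigator sees it, makes him unfit for more treatment.

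After a withdrawal, "the Investigator will make every effort to complete the End of Treatment/follow-up procedures specified in the Schedule of Events".

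Section 6 (Aim 1.1, Analysis Plan) makes total coronary plaque volume the primary endpoint, measured at baseline and 12 months. The Power paragraph rests on "60 participants (30 in each comparative treatment arm) with both baseline and month 12 CCTA". Section 12 sets accrual at 30 per arm and predicts low dropout without a figure. Under Other statistical considerations in Section 6, the intent-to-treat population is defined thus: "Patients who are evaluable for safety and who are furthermore evaluable at 12-month CCTA assessment will be considered evaluable for correlative biomarker analyses". No method for missing scans is given.

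**The concern.** Stopping a treatment and leaving a study are different events. Section 14 treats the first as a reason for the second. A man taken off ADT at month 4 for an adverse event meets a criterion that ends his participation, yet his primary-endpoint measurement is due eight months later. If the scan is not taken, no later choice of analysis set can recover it.

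The loss could differ between the randomised arms for three reasons that the protocol itself supplies:

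- The trial is open-label (Section 1), and one criterion rests on the investigator's judgment.
- Section 5 describes a drug diary and medication reconciliation for relugolix only, so noncompliance may be detected more readily there.
- Section 3 reports more major cardiovascular events on a GNRH agonist than on relugolix from as early as 4 weeks. Such events, if judged treatment-related and unacceptable, fall under the adverse-event criterion.

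The comparison could then drift from all randomised men towards men who tolerated and adhered to their drug.

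**Working it through.** **Inputs.** From Section 6, Power: SD of change 30 mm³, target difference 20 mm³, 30 per arm with both scans, 80% power. From Section 12: 30 accrued per arm. Assumed, because not documented: alpha 0.05, the withdrawal rates, and the excess plaque change in unscanned men.

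**1. The plan's own figure.** With 30 per arm, difference 20 and SD 30, t-test power is 81.8% one-sided and 71.9% two-sided. The stated 80% is therefore reproduced only with a one-sided test; the plan does not state sidedness. The Power paragraph also gives P(X>Y) = 0.72. With that value, Noether's two-sided formula needs 54 men in total, and 54/0.9 = 60. One could guess that 60 hides a 10% allowance, but the text says that the 60 are men with both scans.

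**2. Slack.** Accrued 30, needed with both scans 30, so the stated allowance is 0 per arm. To end with 30 scanned per arm, enrolment would have to be 32, 34, 36 or 38 per arm at 5%, 10%, 15% or 20% loss.

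**3. Balanced, uninformative loss.** SE of the difference = 30 × √(2/n).
- n = 30: 30 × √(2/30) = 7.7 mm³.
- n = 27 (10% loss): 30 × √(2/27) = 8.2 mm³.
- t-test power at 10% loss falls from 81.8% to 78.0% one-sided, or from 71.9% to 67.2% two-sided. Only precision suffers.

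**4. Informative loss in one arm (illustration).** Let a fraction f of GNRHa men be unscanned, none on relugolix, and let the unscanned men's mean change be 30 mm³ (one planned SD) above that of scanned men. The full-arm mean exceeds the scanned mean by f × 30.
- f = 0.10: 0.10 × 30 = 3 mm³; 3/20 = 15% of the target.
- f = 0.20: 0.20 × 30 = 6 mm³; 6/20 = 30% of the target.

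If the 30 mm³ excess is instead measured from the full-arm mean, the shortfall is 30f/(1 − f), and the observed difference is 20 − 30f/(1 − f).
- f = 0.10: 20 − 3.3 = 16.7 mm³; normal-approximation power 67% one-sided, 55% two-sided.
- f = 0.20: 20 − 7.5 = 12.5 mm³; power 45% one-sided, 33% two-sided.
- No loss, same approximation: 82.6% one-sided, 73.3% two-sided.

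**5. Sensitivity.** With f = 0.10 and an excess of 15 mm³ over the full-arm mean, the observed difference is 18.3 mm³ (power 75% one-sided, 63% two-sided). If the loss in step 4 fell on relugolix instead, with the 30 mm³ excess over scanned men, the relugolix mean would be 3-6 mm³ too low and a true difference of 20 would appear as 20 + 3 = 23 to 20 + 6 = 26 mm³. The sign of the bias depends on which arm loses men and on which men they are.

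**6. Does the safeguard reach the scan?** Section 6 puts ADT duration at 6-24 months, so end of treatment need not fall at month 12, and after early withdrawal it precedes it. The follow-up procedures are defined by reference to a Schedule of Events, and no other section says that they include the month-12 CCTA.

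**The case against.** The strongest reply is that the scan is not forfeited. Section 14 itself asks for every effort at follow-up procedures after withdrawal, and Section 6 schedules the second CCTA for each patient in each cohort at 12 months from ADT initiation, not at the end of treatment. Men on 6-month ADT are scanned off drug anyway. The Schedule of Events is not in the text available for review; its absence is not counted as an error, and nobody can say that it omits the scan. This stands as far as it goes: a reader might infer that the scan is lost, but the documents support only that it is not assured.

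The plan also shows some tolerance for interrupted treatment. Section 5 provides for restarting relugolix after more than 7 missed days, and Section 19 records permanent discontinuation as an action taken for an adverse event. So ordinary missed doses need not mean withdrawal. Neither section, however, overrides the Section 14 list or says that such men keep the month-12 scan.

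A reader might also infer that a late study CCTA triggers withdrawal. The imaging phrase in the noncompliance criterion does not name the study CCTA and sets no number of days, and Section 7 allows 12-15 months for the final draw. The phrase is ambiguous and should be clarified; it does not establish that late scans are discarded.

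Finally, the illustration assumes one-sided loss and a full-SD excess, neither of which is documented, and a 3-6 mm³ bias is below one standard error (7.7 mm³). That is fair, and is why it is offered only as an illustration.

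**Conclusion.** The point holds in this form: Section 14 ends study participation for treatment-related reasons, offers no off-treatment, on-study status, and leaves the month-12 primary-endpoint scan to a best effort not tied to that scan. With no stated allowance for loss in an open-label trial, this exposes the randomised comparison to loss that may depend on arm and possibly on outcome.

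The size is unknown. Under the stated assumptions it ranges from a small loss of precision (SE 7.7 to 8.2 mm³ at a balanced 10%) to a 3-6 mm³ bias, 15-30% of the target, at 10-20% loss confined to GNRHa.

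It is tempting to add that the men removed are those most informative about cardiovascular toxicity, and that the effect will be understated. The documents do not support that. The criterion covers any unacceptable treatment-related event, no section links withdrawal to plaque change, and losses for noncompliance could fall on the relugolix arm. The direction is unsettled.

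**What to change.** Amend Section 14 as follows.

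- **Discontinuation of study treatment.** Move the existing treatment-related reasons here, with their clinical content unchanged.
- **Withdrawal from the study.** Limit this to withdrawal of consent, death or loss to follow-up.
- **Continued follow-up.** State that all other enrolled men stay on the original calendar for the 3-, 6- and 12-month draws and the 12-month CCTA, unless CT acquisition is no longer feasible for reasons such as those in the Section 10 exclusions (renal insufficiency, contrast allergy, arrhythmia).
- **Late imaging.** Clarify that the imaging wording in the noncompliance criterion does not make a late study CCTA a reason for withdrawal. A late scan is acquired, dated and kept.

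The cost is a wording amendment. Two scans and four draws are already planned for every man, and participant payments for both scans are already provided for; the documents do not state how the scans themselves are funded. The downside is that coordinators follow some men who are off study treatment. The change helps only men whose month-12 scan has not yet been missed, so it should be made early.

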Men with localized intact PCa, or non-metastatic recurrence following prostatectomy, and prescribed radiation therapy (XRT) with or without concomitant ADT will be consented and enrolled on this prospective trial. Eligible subjects are men > 18 years old diagnosed with non-metastatic PCa planning to undergo curative-intent therapy. Men with prior cardiac stent or bypass surgery will be excluded. Men with prior exposure to ADT will be excluded.

Each patient will undergo external beam XRT with or without concomitant ADT of 6-24 months duration. **For those men with National Comprehensive Cancer Network (NCCN)-defined unfavorable intermediate- or high-risk disease, or with biochemically recurrent PCa requiring salvage XRT plus ADT, each will be randomized 1:1 between injectable intramuscular or subcutaneous GNRHa depot (leuprolide 22.5 mg every 3 months, leuprolide 45 mg every six months) versus GNRH-antagonist (oral relugolix 360 mg loading dose followed by 120 mg daily).** Men with NCCN-defined low- or favorable intermediate-risk intact disease, or those with biochemically recurrent PCa requiring salvage XRT without ADT, will be treated with XRT alone. Each patient will provide consent for (1) pre-treatment and 12-month post-ADT prospective ECG-gated, contrast-enhanced CCTA and (2) peripheral blood banking at baseline and at 3-, 6-, and 12-months post-treatment (**Figure 5**).

Figure 5. Study Schema

ADT randomization will be created using preconstructed allocation sequences using maximal randomization (<https://ctrandomization.cancer.gov/tool/>). Patients will undergo a pre-randomization stratification based on Atherosclerotic Cardiovascular Disease (ASCVD) risk score (low/intermediate versus high). All principal investigators and co-investigators will be blinded to this randomization block. Lead statistician ([name]) and clinical research coordinators will have access to this allocation sequence.

Methods: As seen in above study schema, each patient in each cohort will undergo pre-treatment and 12-month post-ADT initiation coronary CT. Each patient will undergo a non-contrast CT scan using standard

Protocol Title: Mechanism and Predictors of Cardiotoxicity after Prostate Cancer Treatment: A Parallel Cohort and Randomized Trial Comparing Radiation Alone, Radiation plus Leuprolide, and Radiation plus Relugolix

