Based on current prostate cancer volume at Winship Cancer Institute, accrual is expected to be complete in 12 months. Specifically, approximately 40 new patients with localized intact or recurrent PCa eligible for XRT (with or without ADT) are seen at all Winship sites monthly. We predict an enrollment rate of 20% with a low dropout rate, given that the final blood draw and coronary CT will occur 12 months after treatment initiation, which corresponds to the time of first or second standard post-treatment follow up appointment after completion of therapy.

Clinical research coordinators will screen all prostate cancer radiation oncology providers (directed by PI [name]) for all eligible patients to enroll. Co-investigators will be responsible for consenting patients in radiation oncology clinic.

13. Recruitment Methods

Patients will be recruited from those seen at the Department of Radiation Oncology at Winship Cancer Institute (EUH, EUHM, ESJH, EPTC). A brief description of the study will be given verbally to the patients, followed by written informed consent, and any relevant supplemental material as needed. The patients will be given ample time to review the consent and a time for questions and answer will be provided.

Study Enrollment Procedures

A copy of the institution's IRB-approved informed consent document and written justification for any changes made to the informed consent for this protocol must be on file at the Online Collaborative Research Environment (OnCore, <https://oncore.emory.edu>) and available to the Emory University Office for Clinical Research) before any patients may enter. The Winship Cancer Center institution consent form must be reviewed and approved and all documents must be received (i.e., IRB approved documentation, IRB approved consent form, etc.).

Patient Registration

All patients entering this study will be registered with the Clinical Trials Office (CTO) at the Winship Cancer Institute, Atlanta, GA. The CTO is open Monday through Friday from 8am-5pm (EST). OnCore will be used to record information for all registered patients including their assigned patient ID.

Study personnel will notify Winship Central Subject Registration (WCSR) by email at [contact], once subject has been consented for a trial.

Email notification must be done within 24 hours after consent has been obtained and it will include scanned copies of:

- Signed patient consent form
- HIPAA authorization form

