Financial incentive will be provided for each patient to account for additional travel time and transportation (e.g. vehicle gas) associated with non-standard coronary CT on study (\$100 Visa gift card after

Protocol Title: Mechanism and Predictors of Cardiotoxicity after Prostate Cancer Treatment: A Parallel Cohort and Randomized Trial Comparing Radiation Alone, Radiation plus Leuprolide, and Radiation plus Relugolix

completion of each scan; total \$200 eligible per patient). Gift cards will be distributed to patients by mail after completion of each coronary CT scan (i.e. pretreatment, 12-month).

18. Data Management and Confidentiality

All blood and data are deidentified or coded under the existing IRB-approved protocol described above before they are used in this study. Data cannot be linked to an individual other than by a biorepository or Honest Broker delegate. Investigators on this protocol will be responsible for the management of study data and specimens and disposal upon completion of this study.

Clinical, imaging, blood analyses data will be stored in a password protected REDCap database. Access to stored data will be limited by personnel "roles" and comply with minimum necessary standards. Emory physicians on this study and their designees may access and use PHI to determine if patients are eligible to participate in this study and may also access PHI to assist with preparation of data for research. By limiting access to data through physical and cyber procedures, the risk of the improper release of PHI will be reduced. Appropriate administrative, technical, and physical safeguards to protect patient data will be implemented. Winship employees are trained in the protection of patient privacy; such training will be modified as needed to address privacy and security issues arising from new systems and processes created for this study.

19. Provisions to Monitor the Data to Ensure the Safety of Participants

Adverse Events (AEs)

From the time of treatment allocation through **30** days following cessation of treatment, all adverse events, that begin or worsen after informed consent, must be recorded by the investigator or designee at each examination on the Adverse Event case report forms/worksheets.

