The investigator will make every attempt to follow all subjects with non-serious adverse events for outcome. Conditions that were already present at the time of informed consent should be recorded in the Medical History page of the patient's CRF/worksheet.

Adverse events will be assessed and graded according to the Common Terminology Criteria for Adverse Events (CTCAE) version 5.0

(http://ctep.cancer.gov/protocolDevelopment/electronic_applications/ctc.htm). Grade 1 to 5 will be used to characterize the severity of the Adverse Event. If CTCAE grading does not exist for an adverse event, the severity of mild, moderate, severe, and life-threatening, death related to the AE corresponding respectively to Grades 1 - 5, will be used. The occurrence of adverse events should be sought by non-directive questioning of the patient during the screening process after signing informed consent and at each visit during the study. Adverse events also may be detected when they are volunteered by the patient during the screening process or between visits, or through physical examination, laboratory test, or other assessments. As far as possible, each adverse event should be evaluated to determine:

1. The severity grade (CTCAE Grade 1-5)
2. Its duration (Start and end dates)
3. Its relationship to the study treatment (Reasonable possibility that AE is related: No, Yes) or Its relationship to the study treatment (Reasonable possibility that AE is related: No, Yes, investigational treatment, Yes, the study treatment (non-investigational), Yes, both and/or indistinguishable)
4. Action taken with respect to study or investigational treatment (none, dose adjusted, temporarily interrupted, permanently discontinued, unknown, not applicable)
5. Whether therapy was given (no concomitant medication/non-drug therapy, concomitant medication/non-drug therapy)
6. Whether it is serious,
7. Outcome (not recovered/not resolved, recovered/resolved, recovering/resolving, recovered/resolved with sequelae, fatal, unknown).

Protocol Title: Mechanism and Predictors of Cardiotoxicity after Prostate Cancer Treatment: A Parallel Cohort and Randomized Trial Comparing Radiation Alone, Radiation plus Leuprolide, and Radiation plus Relugolix

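### If the 30-day rule sets the adverse-event collection period, the by-arm AE summaries observe the radiation-alone cohort for less time than the ADT arms (minor)

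*Combined protocol and SAP*

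**What the plan says.** All references are to the combined protocol and SAP.

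- **Section 19, Adverse Events, opening paragraph.** Mandatory recording starts at treatment allocation and has a 30-day limit: "days following cessation of treatment, all adverse events, that begin or worsen after informed consent, must be recorded by the investigator or designee". Cessation is not defined for any group.
- **Section 19, later in the same part.** AEs should be sought by non-directive questioning "during the screening process after signing informed consent and at each visit during the study". No end tied to treatment is given here. A later paragraph requires an AE already detected to be followed until it resolves or is judged permanent.
- **Section 6, Procedures Involved.** "Each patient will undergo external beam XRT with or without concomitant ADT of 6-24 months duration". The remaining men receive radiation alone, and no length is given for the radiation course.
- **Sections 9 and 12.** Every man is on study for about 12 months, and "the final blood draw and coronary CT will occur 12 months after treatment initiation".
- **Section 6, Other statistical considerations.** The radiation-alone cohort is in the safety population, and "tabulated summaries of categorized AEs will be generated for all patients collectively and will be summarized by arms". No common observation period or person-time denominator is stated.
- **Section 14.** On withdrawal, "the Investigator will make every effort to complete the End of Treatment/follow-up procedures specified in the Schedule of Events". That schedule is not in the text available for this review, so it cannot be checked whether it fixes the AE period.

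**The concern.** The opening rule of section 19 ties the AE observation period to the length of treatment, and treatment length is what separates the groups: a radiation course alone, or radiation with 6-24 months of ADT. All three groups stay on study for about the same year, yet under that rule the obligation to record new AEs ends at different times.

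The safety tables then place the groups side by side without saying how long each was observed. Radiation alone could show fewer AEs than the ADT arms simply because recording stopped sooner. A reader of those tables could take the difference for a treatment effect.

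If AEs are instead recorded at every visit to month 12 in all groups, the imbalance largely disappears. The plan should therefore say which statement sets the period.

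**Working it through.** The documents state no AE observation time, so there is no planned figure to reproduce. The check is arithmetic on windows.

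**Inputs from the documents**
- Mandatory window ends 30 days after treatment stops (section 19).
- ADT lasts 6-24 months (section 6).
- Time on study is about 12 months (section 9).

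**Assumptions**
- A year is 365.25 days and a month is 30.44 days.
- ADT is given for its planned length and is the last treatment to end.
- The radiation course lasts 1-9 weeks (7-63 days); the documents give no length.
- The lag from allocation to start of treatment is 0 days, then 60 days in both groups as a sensitivity case.

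**Formula.** Window = lag + treatment length + 30 days, capped at the study year.

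**No lag**
- 6-month ADT: 182.6 + 30 = 212.6, about 213 days; 212.6 / 365.25 = 58% of the year.
- ADT length that covers the full year: (365.25 - 30) / 30.44 = 11.0 months.
- Radiation alone, 1 week: 7 + 30 = 37 days; 37 / 365.25 = 10%.
- Radiation alone, 9 weeks: 63 + 30 = 93 days; 93 / 365.25 = 25%.
- Ratio, 6-month ADT to radiation alone: 212.6 / 93 = 2.3, up to 212.6 / 37 = 5.7.
- Ratio, full-year ADT to radiation alone: 365 / 93 = 3.9, up to 365 / 37 = 9.9.

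**60-day lag in both groups, against 6-month ADT**
- 6-month ADT: 212.6 + 60 = 272.6 days.
- Radiation alone: 37 + 60 = 97 days, to 93 + 60 = 153 days.
- Ratio: 272.6 / 153 = 1.8, up to 272.6 / 97 = 2.8.

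**How far the result depends on the assumed radiation length**
- For equal windows, radiation + 30 must equal 182.6 + 30, so the course would have to last about 183 days. A lag common to both groups cancels.
- For the no-lag ratio to fall below 2, the course would have to exceed 212.6 / 2 - 30 = 76 days.

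The direction therefore holds for any radiation course shorter than about 6 months. Only the size depends on the assumptions.

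**Under one common 12-month period**, each group is observed for about 365 days and the ratio is 1.0.

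**The case against.** The strongest reply is that the two statements in section 19 are compatible: the first sets a mandatory period, the second describes how AEs are to be found. The first does not forbid recording later events, and the follow-up of detected AEs shows that assessment continues at visits without a 30-day limit. This stands in part, because a flat contradiction is not shown. It does not remove the point. If the first statement sets the period and the second only the method, the unequal windows follow directly. Following a detected AE to resolution does not extend the period for new ones.

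The Schedule of Events may settle the matter. It is not available, so nothing is claimed about its content.

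Little rests on the affected tables, and this stands. Section 6 plans summary statistics for AEs and no formal safety stopping rule. The radiation-alone cohort is non-randomised and selected for lower-risk disease or salvage without ADT, so its AE counts would not be causally comparable even with equal windows. Section 16 expresses interest in the comparative toxicity of ADT regimens, which is the randomised contrast.

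Three stronger readings are tempting, and the documents do not support them:

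- *That leuprolide versus relugolix is biased.* Section 5 gives both arms the same rule for duration, by risk category, so their windows are equal in expectation. This needs cessation to be dated the same way for depot injections ("leuprolide 22.5 mg every 3 months, leuprolide 45 mg every six months" in section 6) and daily tablets. Section 19 leaves that open but does not say that the dating differs.
- *That serious cardiovascular events would be missed.* The SAE text gives a 24-hour reporting deadline and no collection period. That is silence, not evidence of loss.
- *That a known share of AEs, or of planned contacts, falls outside the window.* No AE rate is given, and no available text makes the scheduled blood draws AE examinations.

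**Conclusion.** The point holds conditionally and is minor. If the 30-day rule sets the collection period, radiation alone is observed for about 37-93 days, against about 213 days for 6-month ADT and the full year for ADT of about 11 months or more. The ratio against 6-month ADT is about 2.3-5.7 with no lag and about 1.8-2.8 with a 60-day lag. The radiation length and the lag are both assumptions.

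What is affected is the descriptive AE comparison of the non-randomised cohort with the ADT arms. The CCTA endpoints are measured at fixed times and do not depend on the AE window.

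**What to change.** - **Section 19:** reconcile the two statements. Record AEs and SAEs in all three groups from one defined start through the 12-month CCTA visit, whenever treatment ends. Consent is one possible start; treatment allocation has no evident counterpart in the non-randomised cohort.
- **Section 19:** keep the existing collection, to 30 days after cessation, for men still on ADT after that visit, outside the common-window tables. Define cessation so that it is dated the same way for depot and oral drug.
- **Section 6, Safety Analysis:** tabulate AEs by group over the common 12-month window, and show observation time for men who leave early. Label radiation alone versus ADT as descriptive and non-randomised.

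The cost is a wording change and some extra AE entry, mostly in the radiation-alone cohort, who already attend for the 12-month scan. No existing safety collection is reduced.
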